1. RISKS TO THE SUBJECTS

a. Human Subjects Involvement and Characteristics

- Describe the proposed involvement of human subjects.

- Describe the characteristics of the subject population, including their anticipated number, age range and health status.

The overarching aims of this pilot project is to provide preliminary evidence on the cost-effectiveness of a lay patient navigator/care coordinator for patients with SLE, targeting inpatient admissions to prevent readmissions as a marker of failed self-management. Our rationale is that a lay patient navigator/care coordinator integrated into the health care team to provide modeling and reinforcement to SLE patients will encourage patients to engage in activities that promote the learning of disease self-management skills and support their practice of these learned skills. This will lead to improved health-related quality of life, self-management, and disease activity and associated reductions in healthcare costs.

Patient eligibility criteria: The study inclusion and exclusion criteria are as follows:

Inclusion criteria for SLE patients include: 1) Hospital admission for SLE-related issue; 2) clinical diagnosis of systemic lupus erythematosus (SLE) from a physician; 3) 18 years of age or older; 4) able to provide informed consent and take part in ongoing assessment/evaluation activities (self-reported questionnaires); 5) able to

commit to duration of study (3 months); 6) able to communicate in English; and 7) have an active phone line (landline or cell phone) for the duration of the study, if agreeing to phone sessions with the lay patient navigator/care coordinator. Exclusion criteria include: 1) cognitive impairment; 2) acute decompensation of chronic conditions precluding participation; 3) conditions that preclude participation in assessments (e.g. blindness or deafness); and 4) terminal illness or life expectancy less than 6 months as evaluated by physician.

Targeted/Planned Enrollment Table

Total Planned Enrollment 40

TARGETED/PLANNED ENROLLMENT: Number of Subjects			
Ethnic Category	Sex/Gender		
	Females	Males	Total
Hispanic or Latino	2	1	3
Not Hispanic or Latino	34	3	37
Ethnic Category: Total of All Subjects*	40		
Racial Categories			
American Indian/Alaska Native	0	0	0
Asian	0	0	0
Native Hawaiian or Other Pacific Islander	0	0	0
Black or African American	29	3	32
White	7	1	8
Racial Categories: Total of All Subjects*	36	4	40

*The "Ethnic Category: Total of All Subjects" must be equal to the "Racial Categories: Total of All Subjects".

- Identify the criteria for inclusion or exclusion of any subpopulation.
- Explain the rationale for the involvement of special classes of subjects, such as fetuses, neonates, pregnant women, children, prisoners, institutionalized individuals, or others who may be considered vulnerable populations. Note that 'prisoners' includes all subjects involuntarily incarcerated (for example, in detention centers) as well as subjects who become incarcerated after the study begins.
- If you propose to exclude any sex/gender or racial/ethnic group, include a compelling rationale for the proposed exclusion. For example, 1) the research question addressed is relevant to only one gender or 2) evidence from prior research strongly demonstrates no difference between genders.
- Provide either a description of the plans to include children or, if children will be excluded from the proposed research, then you must present an acceptable justification for the exclusion. For example, 1) the condition is rare in children as compared to adults or 2) insufficient data are available in adults to judge risk in children.
- List any collaborating sites where human subjects research will be performed, and describe the role of those sites in performing the proposed research.

African Americans display the highest rates of lupus. Due to the exposure of African Americans to a unique trajectory of stressors throughout the life course, it may be critical to test patient navigation as an alternative strategy to improve outcomes in this population. Given the success of the peer mentoring approach in other chronic conditions that disproportionately impact minorities, and its responsiveness to the needs of this unique population, this intervention could result in health improvements that have not been attainable with other interventions. This would significantly reduce disparities and have considerable public health impact.

In the United States, the highest lupus morbidity and mortality rates are among African American women. SLE affects approximately 1 in 250 African American women of childbearing age. Very few men are affected by the disease with a general ratio of 10 females to every 1 male with SLE.

b. Sources of Materials

- Describe the research material obtained from living human subjects in the form of specimens, records, or data.
- Describe any data that will be recorded on the human subjects involved in the project.
- Describe the linkages to subjects, and indicate who will have access to subject identities.
- Provide information about how the specimens, records, or data are collected and whether material or data will be collected specifically for your proposed research project.

1. Research Material & Data: Sources of research material include medical records and research questionnaires.
2. Linkages to Subjects: Subjects will provide identifying information in addition to research data. Paper documents pertaining to this study will be stored in locked file cabinets in both the clinical center and the data

management center, and data will be entered into secure, password-protected web databases developed for this study. A database of name, contact address, telephone number, and other research identification numbers will be stored separate from the study database, for purposes of audit by the MUSC IRB, if necessary. Access to study data will be limited to research personnel.

3. Collection of Data and Specimens:

Personnel: A part-time lay patient navigator will be responsible for consent, enrollment and data collection, a part time health economist will be responsible for accessing and analyzing resource use and cost data, and a part-time data coordinator (DC) will be responsible for data management and analyses for patient reported outcomes. **Data Collection Schedule:** At the baseline visit, the lay patient navigator will give detailed explanation of the study, the reimbursement schedule, and obtain consent. Participants will complete a questionnaire that captures demographics, health literacy, coping, disease activity, disease self-management, anxiety, depression, and quality of life. The lay patient navigator will review study goals, establish the schedule of study sessions, obtain contact information (primary and alternate telephone numbers), and receive study materials. After the baseline assessment, follow-up assessments will be conducted at 6 weeks and 12 weeks. As much as possible, research visits will be scheduled on the same day as their clinic visit.

c. Potential Risks

- Describe the potential risks to subjects (physical, psychological, social, legal, or other), and assess their likelihood and seriousness to the subjects.
- Where appropriate, describe alternative treatments and procedures, including the risks and benefits of the alternative treatments and procedures to participants in the proposed research.

Potential risks to the patient include possible violation of the patient's privacy, discomfort with questions on the research questionnaire, and psychological distress. Details on how these risks will be minimized are discussed under adequacy of protection against risks below.

Confidentiality: This will be maintained by keeping participant folders in locked file cabinets in the research center. Only participants' unique identification numbers will be recorded in folders and on data forms. The database will remain on the MUSC computer system that use unique ID numbers, rather than names, and will be password-protected.

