Overview of Study Design. The Care-coordination Approach to Learning Lupus Self-Management (CALLS) study is a double arm, pre-post pilot designed to examine whether modeling and reinforcement from a lay patient navigator/care coordinator improves disease self-management, indicators of disease activity, health related quality of life (HRQOL), and 30-day readmission in SLE inpatient admissions. We will recruit 40 patients (20 questionnaires and phone sessions and 20 questionnaires only) with active SLE upon hospital admittance at the Medical University of South Carolina (MUSC). The lay patient navigator/care coordinator will be trained to deliver intervention content by twelve weekly telephone sessions carried out across the course of the study. All participants will be assessed using validated measures of patient reported outcomes at baseline, mid-intervention (6 weeks post-enrollment), and immediately following the intervention (12 weeks post-enrollment). Outcomes for patients who agree to phone sessions will be compared with the outcomes of patients who opt to participate in questionnaires only. The study will last 12 months with recruitment and enrollment over 6 months, 3 months for intervention delivery and 3 months for data analysis.

Study Population. The total number of individual patients with systemic lupus erythematosus (SLE) currently being followed by clinicians at MUSC is 1,159 in the past six months that had this encounter diagnosis and 1,526 with this diagnosis in the chart history or problem list or encounter diagnosis, of which approximately 60% are African American and 90% are female. This will allow for the assessment of impact and cost savings/effectiveness according to underrepresented racial and gender categories. The target population for this study will be SLE inpatient admissions. There are approximately 35 SLE and Scleroderma hospital admissions each month, so it is expected that over a 3-month recruitment period, we will be able to recruit 40 participants (20 questionnaires and phone sessions and 20 questionnaires only).

Recruitment of Lay Patient Navigator/Care Coordinator

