Treatment Fidelity. Drs. [name] and [name] will deliver training for the lay patient navigator/care coordinator at the onset of the study. They will be given parameters for their roles and instructed on how to handle potential issues that may arise. After the initial training, the lay patient navigator/care coordinator will continue to meet with the PI weekly to identify challenges and reinforce the guidelines for their role.[185] They will be required to submit logs of the number of calls made, number of hours spent with patients, and content covered during that week. Self-report assessments will be used to track the effectiveness of their services.

Data Collection Schedule. Study questionnaires were carefully chosen based on available evidence of previous validation and their ability to measure key elements of the study aims. The primary method of data collection will be face-to-face interview. All study visits will take place in an MUSC affiliated hospital, the Research Nexus or comparable private location on the campus of MUSC. Indicators of medication adherence will be extracted from the electronic medical records. Financial data will be extracted from the research data warehouse for historical and patient-specific data for cost effectiveness. The MUSC REDCap system will be used for data management.

Primary Outcomes. Primary outcomes of quality of life, self-management, and disease activity (including medication adherence) will be measured using the Lupus Quality of Life Questionnaire (LUP-QOL), which incorporates the Medical Outcomes Study (MOS) Short Form 36 Health Survey (SF-36) and the Functional Assessment of Chronic Illness Therapy-Fatigue (FACIT-F);[187-189] the Patient Activation Measure (PAM), [190,191] which assesses an individual's knowledge, skill, and confidence for managing their health and healthcare; medication refill data in electronic medical records to further validate treatment engagement/adherence; 30-day readmission data to assess cost savings or deficit (compared to historical data from the prior year); and the Systemic Lupus Activity Questionnaire (SLAQ),[192] which is based on items from the physician-rated Systemic Lupus Activity Measure (SLAM) that could be self-reported.[193,194]

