Process Measures and Secondary Outcomes. To assess for differences in outcome expectancy, a modified treatment credibility scale developed by Borkovec and Nau (1972) will be used. Satisfaction with Care will be measured with a previously validated general scale to measure satisfaction/dissatisfaction with health care. Other covariates will be measured by previously validated items from the 2002 National Health Interview Survey [NCHS 2004] to capture age, marital status, education, household income, and health insurance; the Chew Health Literacy Screening Survey[195] to detect potential health literacy problems; the Arthritis Self-Efficacy Scale pain and other symptoms sub-scale, arthritis.[196,197] which measures confidence in one's ability to manage the pain, fatigue, frustration, and other aspects of disease; the PHQ-9, which scores each of the 9 DSM-IV criteria for depression;[198,199] and the 7-item General Anxiety Disorder scale (GAD-7).[200]

Analysis Plan

Aim 1 - Feasibility analyses: Important measures of feasibility will include recruitment, compliance, non-response proportions and participant satisfaction. We will use 95% confidence intervals (CI) for proportions to estimate the proportion of participants who agree to participate out of the number who are initially approached, the proportion who are compliant with the treatment protocol, and the proportion who exit the study prematurely (drop out). In addition, frequency distributions describing the participants' reasons for noncompliance and discontinuation of study participation will be developed. We will also evaluate patient satisfaction with the lay patient navigator/care coordinator services using a likert-type satisfaction scale. For the continuous feasibility measures (e.g. treatment credibility, treatment adherence, phone sessions and attrition), frequency distributions and the median and mean responses (with 95% CIs) will be obtained.

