Participants requiring medical or other professional intervention for study-related events will be provided with appropriate and timely medical guidance by the PI. If adverse events occur during the conduct of this study, they will be reported to the MUSC IRB in accordance with Section 4.7 - Unanticipated Problems and Adverse Events Policy and Procedures.

To protect against the potential risk of loss of confidentiality and/or breach of privacy, data will be compiled using codes in lieu of personal identifiers. Access to study data will be limited to research personnel. Development of and security oversight for the electronic database for this study will be performed by the PI and study statistician. Paper documents pertaining to this study will be stored in locked file cabinets and electronic data will be entered into secure, password-protected databases developed for this study by the research assistants. The PI will perform periodic review of the data entry process to ensure accuracy of recording. When study results are published or presented, only aggregate reports of the results will be used and participants' identity will not be revealed. A file of name, contact address, telephone number, and other research identification numbers will be stored separately on paper and on computer, for purposes of audit by the MUSC IRB, if necessary.

In the event of negative interactions between the lay patient navigator/care coordinator and patients, the following steps will be taken:

1. The PI will communicate with patients and the lay patient navigator on a weekly basis to assess calling patterns, content of calls, any other interactions between the lay patient navigator and patient(s), and any concerns either may have.
2. Patients and the lay patient navigator will be encouraged to contact the PI at any time if they run into a difficult situation with a patient. If during such communication, patient or the lay patient navigator reports that they believe that their patient/lay patient navigator may be depressed, homeless/displaced, suicidal, has broken confidentiality, is repeatedly asking for medical advice, prying too much into their personal life, or that they are simply not connecting, the PI will meet with each party individually to discuss, troubleshoot, and develop solutions or direct to services, when applicable.

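### The navigator who delivers the intervention is also the only named collector of study data, mainly by face-to-face interview, which leaves the self-report outcomes open to bias that differs by arm

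*Protocol*

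**What the plan says.** **Who collects.** Section E.1.b (Sources of Materials, Personnel) says: "A part-time lay patient navigator will be responsible for consent, enrollment and data collection". The same section has the navigator run the first visit: "At the baseline visit, the lay patient navigator will give detailed explanation of the study, the reimbursement schedule, and obtain consent". The other two roles listed there are a health economist, for resource use and cost, and a data coordinator, for managing and analysing the patient-reported outcomes. Neither is given collection.

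**Who delivers.** Section D, Overview of Study Design: "The lay patient navigator/care coordinator will be trained to deliver intervention content by twelve weekly telephone sessions". Only the intervention arm receives these sessions.

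**How.** Section D, Data Collection Schedule: "The primary method of data collection will be face-to-face interview". Against this, the inclusion criteria call the assessments self-reported questionnaires, the arms are described by whether patients complete questionnaires with or without phone sessions, and E.1.b says that participants complete a questionnaire at baseline.

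**When.** E.1.b: "After the baseline assessment, follow-up assessments will be conducted at 6 weeks and 12 weeks". The sentence names no assessor.

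**What.** Under Primary Outcomes, LUP-QOL, PAM and SLAQ are self-report; refills and 30-day readmissions come from records. The secondary measures include a treatment credibility scale. The Aim 1 analysis adds: "We will also evaluate patient satisfaction with the lay patient navigator/care coordinator services using a likert-type satisfaction scale".

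**The concern.** The person to whom patients would report their quality of life, activation and disease activity knows the arm and has a weekly supportive relationship with one arm only. Patients tend to give more favourable answers to someone who has been helping them. Here that tendency would act in the intervention arm and have no counterpart in the control arm, so it cannot be separated from a treatment effect. The satisfaction and credibility ratings are the most exposed, because they concern the interviewer's own work.

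The navigator also has a stake in the answers. Treatment Fidelity in section D uses the self-report assessments to judge how well the navigator's services work, and E.2.b provides for ending the study if several patients are unhappy with the navigator.

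Aim 2 exists to supply effect sizes for a future R01-level trial. A bias built in at collection passes into that calculation, and no later analysis can remove it.

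**Working it through.** The point concerns roles and rests on no figure in the protocol, so the main check is to set the sections side by side.

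1. *Collector.* E.1.b gives data collection to the navigator. The other staff mentioned are the data coordinator and health economist (E.1.b), the research personnel trained to recognise a positive PHQ-9 screen, and the research assistants mentioned in connection with the databases (both E.2.b). None is assigned to collect the study outcomes.
2. *Deliverer.* Overview of Study Design and Phone sessions (section D) give the weekly sessions to the same role.
3. *Mode.* Data Collection Schedule makes interview primary, while the eligibility criteria and E.1.b use the language of questionnaires completed by participants. The plan does not reconcile the two.
4. *Timing.* Recruitment of SLE patients (section D) places consent before assignment and the baseline assessment after it. Arm can therefore be known at every assessment, but the weekly relationship exists only from week 1 on. Weeks 6 and 12 are the exposed visits.
5. *Scope.* LUP-QOL, PAM, SLAQ, satisfaction and credibility are exposed. Refills, readmissions and cost are not.

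**Illustration of size.** The protocol gives no value for the bias, so the values of b below are assumptions.

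First, the plan's own precision figure. With 20 per arm, the SD of change is SD × √(2(1 − r)). For r = 0.5 this is 1.00 SD, and the between-arm half-width is t(0.975; 38 df) × 1.00 × √(2/20) = 2.024 × 0.316 = 0.64 SD, as stated in Sample Size Justification. For r = 0.25 (AR(1) with ρ = 0.5 over two intervals) the SD of change is 1.22 SD and the half-width 0.78 SD. Which r applies is a separate matter, so both are shown.

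With true difference zero and a shift b favouring the intervention, coverage = Φ(1.96 − b/SE) − Φ(−1.96 − b/SE), where SE = 0.316 SD (r = 0.5) or 0.387 SD (r = 0.25):

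| b (SD, assumed) | coverage, r = 0.5 | coverage, r = 0.25 |
|---|---|---|
| 0.1 | 0.938 | 0.942 |
| 0.2 | 0.903 | 0.919 |
| 0.3 | 0.842 | 0.879 |
| 0.4 | 0.756 | 0.822 |

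**Effect on sizing the next trial.** Suppose, purely as an example, a true effect of 0.3 SD of change, 80% power and two-sided 5%. Then n per arm = 2 × (1.96 + 0.8416)² / d² = 15.70 / d². The correct size is 15.70 / 0.09, or 175 per arm. If the pilot's average estimate is raised by b:

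- b = 0.1: d = 0.4, n = 99, true power Φ(0.3 × √(99/2) − 1.96) = 0.56
- b = 0.2: d = 0.5, n = 63, true power Φ(0.3 × √(63/2) − 1.96) = 0.39
- b = 0.3: d = 0.6, n = 44, true power Φ(0.3 × √(44/2) − 1.96) = 0.29

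These figures show how a bias would carry through. They do not estimate one.

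**The case against.** Several objections have force.

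- *The key step is inferred.* The sentence on weeks 6 and 12 is passive, and nothing says who hands out the satisfaction or credibility scales. A reader might take it as stated that the navigator interviews every patient at every visit and takes ratings of their own service in person. The text does not go that far. It assigns data collection to the navigator, names no one else, and prefers interview. What stands is that following the plan as written leads there.
- *Self-completion may already be intended.* The questionnaire wording supports this, but the Data Collection Schedule says otherwise, so the two need reconciling.
- *There are other channels for satisfaction.* E.2.b tracks it through weekly calls, whose caller is not named, and has the principal investigator in weekly contact with patients. These serve to detect problems; they do not replace the Aim 1 scale. They do make it too strong to call the satisfaction result worthless.
- *Control contamination.* A reader might add that contact with the navigator contaminates the control arm. The support is thin: consent comes before assignment, administering a questionnaire is not the twelve-session programme, and contamination would tend to shrink the difference rather than inflate it.
- *The interval is wide.* A shift of 0.1 to 0.3 SD is less than half of the 0.64 SD half-width. That is true, but imprecision does not cancel bias, and the point estimate is what would be carried forward.

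**Conclusion.** The point holds in limited form. The protocol gives data collection to the person who delivers the intervention, names no other collector and prefers face-to-face interview. The self-report outcomes and, by inference, the ratings of the navigator's service are therefore open to bias that differs by arm and feeds the Aim 2 effect sizes. Record-based outcomes are outside the point.

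The size is unknown. The coverage and sample-size figures rest on assumed shifts of 0.1 to 0.4 SD, a normal approximation and 20 per arm. A reader might set such a shift beside the effect sizes above 0.3 reported for the PALS pilot and conclude that bias alone could reproduce them. The documents do not support that comparison: PALS had no control arm, so its figures are changes over time and not differences between arms.

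This is a cheap improvement, best made before data collection because it cannot be repaired afterwards.

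**What to change.** In Data Collection Schedule (section D) and in E.1.b, state that:

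- the self-report questionnaires, at least at weeks 6 and 12 and always for satisfaction and credibility, are completed by the patient without the navigator present, for example directly in REDCap;
- where help or reading aloud is needed, it comes from research personnel already named. The research assistants are one option: E.2.b mentions them where it says "electronic data will be entered into secure, password-protected databases developed for this study by the research assistants", so this task would have to be assigned to them explicitly. The data coordinator, who analyses these outcomes, is preferably not used;
- the navigator does not see satisfaction or credibility answers by patient.

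The navigator can keep consent and enrolment, which precede assignment. Barring the navigator from all contact with control patients is not needed and would leave those tasks without an owner. Use of the other assessments to guide the sessions can continue, and the PHQ-9 safety pathway in E.2.b stays as it is.

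*Cost.* Protocol wording and some reallocated staff time, for at most 40 × 2 = 80 assessments at weeks 6 and 12, or 40 × 3 = 120 if baseline is included. REDCap is named only for data management, so patient entry would have to be set up; paper would also serve. Missing items may rise where health literacy is low, a problem the protocol already screens for. Patients still know their arm, so this removes the interviewer's part of the response bias and not all of it.
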